2.0 STUDY OBJECTIVES

2.1 Although multiple strategies for increasing physical activity have proven efficacious, little is known about the optimal intervention strategies for breast cancer survivors or how those interventions can be effectively implemented in real-world settings. The proposed pilot project will assess the implementation of evidence based strategies for increasing physical activity among breast cancer survivors. Results from this pilot project will support future grant applications. These future studies will utilize multi-phase optimization strategy (MOST) to identify the optimal combination of intervention strategies to increase physical activity among breast cancer survivors.

Aim 1. Evaluate the feasibility of screening and subject recruitment through targeted mailings to breast cancer survivors using the UT Southwestern cancer registries.

Aim 1A. Assess the percentage of contacted survivors completing online questionnaires.

Aim 1B. Assess the percentage of respondents meeting eligibility criteria (< 150 minutes of physical activity per week and ≥ 8 on the PHQ-9).

Aim 1C. Assess the percentage of eligible respondents enrolled in the physical activity intervention.

Aim 2. Evaluate the feasibility of implementing a multi-component physical activity intervention in breast cancer survivors with significant depressive symptoms.

Aim 2A. Physical activity program compliance.

Aim 2A.a. Assess the percentage of physical activity classes attended

Aim 2A.b. Assess the percentage of days of use of the self-monitoring device

Aim 2B. Participant-reported program satisfaction

Aim 3. Conduct preliminary analysis of changes in physical activity and depressive symptoms following the physical activity intervention.

Hypothesis 1. Participants in the physical activity program will demonstrate increases in physical activity at three and six months

Hypothesis 2. Participants in the active living program will demonstrate decreases in depressive symptoms at three and six months post-baseline.

Cancer Relevance: This project simultaneously targets two factors (depression and inactivity) related to poor outcomes in breast cancer survivors and provide important information on how to effectively address these risk factors in a real-world setting.

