5.4 Treatment and Study Intervention

Participants will be enrolled in the physical activity intervention described in sections 7.0 Assessments will be conducted based on the schedule outlined in section 6.0. Qualified, trained, and certified personnel will conduct clinician-rated assessments (all assessments which are not self-report). During the trial, the outcome assessments will be obtained at Weeks 1, 13, and 25. Participants will be asked to wear an accelerometer during Weeks 1, 13 and 25. If the participant is not able to come to the site and (s)he agrees, some assessments and/or visits may be conducted by phone, by mail, or at appropriate off-site locations, and/or on participants' or other off-site computers via the secure study website(s) if access to a computer with internet service is available. Detailed descriptions of the assessments are provided in section 6.0.

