6.2.3 Study Assessments

Measurements of Physical Activity:

Actigraph GT3X+ accelerometer. – The Actigraph will provide a valid and reliable objective assessment of physical activity.²⁴ Subjects will be asked to wear the device for a 7-day period at each assessment time point (baseline and weeks 13 and 25). Subjects will be instructed to wear the device on their non-dominant arm and to remove the device only when it may become submerged in water (bathing, swimming, etc.). Following, the 7-day period, subjects will return the accelerometers using a postage-paid envelope.

Measurement of Psychosocial and Physical Outcomes:

Quick Inventory of Depressive Symptomatology – Self-Rated (QIDS-SR₁₆). The QIDS-SR₁₆²⁵⁻²⁷ is a 16-item questionnaire to assess severity of depression-specific symptoms. The QIDS-SR₁₆ has high reliability (Cronbach's alpha of 0.83), good concurrent validity (correlations between the QIDS-SR₁₆ and the 17-item Hamilton Rating Scale for Depression is 0.81)²⁵.

Short Form 36 Health Survey (SF-36). The SF-36²⁸ is a 36-item survey of patient-reported general health and quality of life across eight domains of well-being (physical functioning, social functioning, vitality, pain, general health, physical role functioning, emotional role functioning, and mental health).

Pittsburgh Sleep Quality Index (PSQI). The PSQI²⁹ is a 19-item scale designed to assess sleep quality and disturbances. Scores range from 0 to 21 with higher scores representing worse sleep quality. The PSQI has demonstrated reliability (Cronbach's alpha of 0.80) in the assessment of self-reported sleep quality and validity when compared to sleep diaries and polysomnography.³⁰

Brief Fatigue Inventory (BFI). The BFI³¹ is a 9-item scale designed to assess fatigue. The BFI demonstrates good reliability (Cronbach's alpha of 0.96) and validity (correlation of 0.86 with the POMS fatigue subscale).

Functional Assessment of Cancer Therapy – Breast (FACT-B) – The FACT-B³² is a 44-item scale designed to measure multidimensional quality of life in breast cancer patients. The FACT-B has demonstrated reliability (Cronbach's alpha of 0.90) and concurrent validity (0.87 correlation with the Functional Living Index-Cancer and 0.86 correlation with the Functional Assessment of Cancer Therapy-General).

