8.0 STATISTICAL ANALYSES

8.1 Primary Analyses

Based on recommendations of Leon et al.,⁴⁰ the Aims 1 and 2 will examine the feasibility of implementing a physical activity intervention for breast cancer survivors. The feasibility of the study will be assessed by the following criteria:

- 1) Screening - the number of subjects screened through the web-based questionnaire and the percentage of those screened who meet program eligibility requirements
- 2) Recruitment - the percentage of screened subjects that are ultimately enrolled
- 3) Intervention Compliance – defined as percentage of weekly exercise does completed by participants randomized to the exercise condition
- 4) Retention – defined as percentage of assessments completed

Consistent with Aim 3, we will conduct a data analysis examining the effects of the intervention on physical activity and depressive symptoms. A mixed-effects repeated measures model will be used to analyze the primary outcome measures (minutes of MVPA and QIDS-C scores). The independent variables in the model will be time (weeks 1, 13, and 25)(within-subjects factor). The model will allow for random slopes and intercepts while all other factors will be fixed effects. The baseline value of the dependent variable will be included as a covariate as will the other potential covariates if needed [age, race, gender, history of depression]. The need for higher order times terms or the transformation $\log(\text{time}+1)$ to obtain a better fitting model will be considered. The goodness of fit of the final model will be investigated. The analysis will use all available data from all randomized patients with at least one post-baseline visit (i.e., modified “intent to treat” sample) and all tests will be two-sided with alpha of .05 used for significance. The hypothesis will be tested by the significance of the time effect main effect. The analysis will be done using SAS Proc Mixed. Statistical analysis will be completed by [name] within the Center for Depression Research and Clinical Care.

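### The Aim 3 mixed model uses the Week 1 value as both outcome and baseline covariate, and its single time effect does not test change at three and at six months

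*Combined protocol and SAP*

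**What the plan says.** Section 8.1 describes one mixed-effects repeated measures model for each Aim 3 outcome (minutes of MVPA and the QIDS score). Its specification is:

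- Time: "The independent variables in the model will be time (weeks 1, 13, and 25)(within-subjects factor").
- Covariate: "The baseline value of the dependent variable will be included as a covariate".
- Random part: "The model will allow for random slopes and intercepts while all other factors will be fixed effects".
- Form of time left open: "The need for higher order times terms or the transformation" log(time+1) is to be considered, to improve fit.
- Test: "The hypothesis will be tested by the significance of the time effect main effect", two-sided at 0.05.

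Section 5.4 sets the visits: "During the trial, the outcome assessments will be obtained at Weeks 1, 13, and 25". Section 6.2.3 describes the same accelerometer periods as "Subjects will be asked to wear the device for a 7-day period at each assessment time point (baseline and weeks 13 and 25"). The table in section 6.1 has columns for Screening, Baseline, Week 13 and Week 25, and no separate Week 1.

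Section 2.0 states Hypothesis 1 as: "Participants in the physical activity program will demonstrate increases in physical activity at three and six months". Hypothesis 2 states a decrease in depressive symptoms at the same two times. No contrast of Week 13 or Week 25 with baseline is specified anywhere.

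**The concern.** There are two separate faults.

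**Double use of baseline.** Week 1 is the baseline, so the model regresses each participant's Week 1 value on itself. After adjustment the Week 1 row has almost no variance left, while the later rows keep most of theirs. A random intercept, a random slope and a common residual variance cannot describe that pattern, so the standard errors and the test level are unreliable.

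**Test and hypotheses do not match.** The hypotheses name two times and a direction at each. A joint test of time can be significant when change occurred at only one of them. A straight-line slope can miss a real change at three months. What the test means also depends on a form of time that is chosen from the data.

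Aim 3 is the only significance testing in the plan, and section 2.0 says the pilot's results will support later grant applications. Whether any change lasts to six months is what a reader of those applications would want to know.

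**Working it through.** The plan gives no power, SD, correlation or dropout figure for Aim 3, so there is no stated figure to reproduce. From the documents: n=50, one group, three assessment times, two-sided 0.05. Assumed: normal data with baseline SD 1, and correlations written as Week 1–13 / Week 1–25 / Week 13–25.

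**1. What the covariate does to the rows.** Take equal correlation ρ and, for a closed form, a random intercept only. The fitted coefficient on baseline is b = (1 + 2ρ)/3. After adjustment:

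- Week 1 variance: (1 − b)²
- Week 13 variance: 1 − 2bρ + b²
- Week 1–Week 13 covariance: (1 − b)(ρ − b)
- Week 13–Week 25 covariance: ρ − 2bρ + b²

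| ρ | b | Week 1 variance | Week 13 variance | Covariance 1–13 | Covariance 13–25 |
|---|---|---|---|---|---|
| 0.3 | 0.53 | 0.22 | 0.96 | −0.11 | 0.26 |
| 0.5 | 0.67 | 0.11 | 0.78 | −0.06 | 0.28 |
| 0.7 | 0.80 | 0.04 | 0.52 | −0.02 | 0.22 |

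The variance jumps after Week 1 and then stays flat, and the covariance changes sign. A random slope instead lets variance grow with time.

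**2. Error rate of the stated model, categorical time.** REML fits with random intercept and slope, complete data, no true change, and 49 denominator df. The true SE of a change from Week 1 is √[(var₁ + var_k − 2cov)/50]. For the central case 0.6/0.5/0.7:

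- Week 13: √[(2 − 1.2)/50] = 0.126
- Week 25: √[(2 − 1.0)/50] = 0.141

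Results over 2000 data sets:

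| Quantity | With covariate | Reference |
|---|---|---|
| Week 13 SE | 0.105 (17% too small) | 0.126 (true) |
| Week 25 SE | 0.151 (7% too large) | 0.141 (true) |
| Joint time test, false positives | 9.6% | 4.9% (same model without covariate) |

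Smaller repeat simulations of this case gave 9.2% and 10.3% (600 data sets each) and 12.3% (300). Without the covariate they gave 4.0%, 5.7% and 4.7%.

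Six covariances were run: the central case; 0.5/0.4/0.6; 0.6/0.6/0.6; 0.7/0.6/0.75; 0.5/0.5/0.7; and 0.6/0.5/0.7 with follow-up SD 1.4. Across them:

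- the Week 13 SE is 13% to 21% too small;
- the Week 25 SE is 6% to 11% too large;
- joint false positives are 8.7% to 10.0%, against 4.7% to 5.3% without the covariate (Monte Carlo SE 0.7 to 1.0 points).

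The random-effects matrix is at its boundary in 100% of fits with the covariate, against 5% to 56% without it. Allowing an indefinite matrix with non-negative variances (400 data sets) gave a similar 9.5%.

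**3. Linear or log(time+1) coding** (1000 data sets in each of four covariances). The SE is 6.5% to 9.6% too large and false positives are 2.2% to 3.3%, so the direction of the error reverses.

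**4. What a single time effect can show.** Suppose the change is 0.5 SD at Week 13 and zero at Week 25.

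- Weeks 1, 13 and 25 are equally spaced, so the straight-line slope weights are −1, 0, +1. The slope is proportional to Week 25 minus Week 1, which is 0, so the test rejects at its 5% level.
- For a correctly specified 2-df test with equal correlation ρ, the squared deviations of (0, 0.5, 0) sum to 1/6. The noncentrality is 50 × (1/6)/(1 − ρ) = 11.9, 16.7 and 27.8 for ρ = 0.3, 0.5 and 0.7. With 2 and 98 df the power is 0.87, 0.96 and 0.998, although nothing lasts to six months.
- A change at Week 25 only gives the same three values.

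In the planned model (central case, 800 data sets) the joint test is significant in 99.9% of data sets for a Week 13-only change and in 99.1% for a Week 25-only change. A 0.5 SD gain kept at both weeks is detected in 98%, so there is no loss of power for a maintained gain.

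**5. Dropout.** In a random-intercept version with 29% missing at Week 25, depending on the Week 13 value, the covariate produces a Week 25 bias of about −0.03, −0.03 and −0.015 SD for ρ = 0.3, 0.5 and 0.7. Without the covariate it is about 0.

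**The case against.** **The inflated error rate depends on one reading.** With a random intercept only, the joint test stays near 5% with or without the covariate. The random slopes and the log(time+1) option point at least as naturally to continuous time, where the test is conservative. This is fair as to direction, and no single error rate should be quoted as the plan's. But section 8.1 does state random slopes and also calls time a within-subjects factor. Under each coding examined with those slopes, the level is not 5%.

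**Perhaps Week 1 is not meant as an outcome row.** Then time would compare only Week 13 with Week 25, which tests neither hypothesis and contradicts the listed levels.

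**An analyst would notice.** The fit is degenerate, and section 8.1 promises to examine goodness of fit. That may prompt a simplification, but the plan does not say which, and it would be made after seeing the data.

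**Part of the SE error is not due to the covariate.** This stands. Without it, the random intercept and slope structure still makes the Week 13 SE 2% to 11% too small.

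**Any omnibus test fails to locate an effect, and higher-order time terms may be added.** Both true, but the hypotheses name the times and no follow-up contrast is specified.

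**Aim 3 is preliminary in a feasibility pilot.** This stands and limits the severity.

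**Conclusion.** Both faults hold. The double use of baseline and the missing contrasts follow from the text alone. The size of the error rests on assumptions that the documents cannot confirm: normal data, n=50 complete, and correlations of 0.4 to 0.75. Under those, the joint test of categorical time has a level of about 9% to 10% instead of 5%, while linear or log time gives about 2% to 3%. With complete data the estimated changes are not biased. Whichever coding is used, a significant time effect does not show whether activity or mood changed at three months, at six months, or at both. No sample size or feasibility criterion depends on this test, so the point should be fixed but is not critical to the pilot.

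**What to change.** In section 8.1:

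1. Keep Weeks 1, 13 and 25 as outcomes, with time as a three-level categorical factor.
2. Remove the baseline value of the outcome as a covariate.
3. Replace the random slope and the data-driven form of time with an unstructured 3×3 covariance (REML, Kenward-Roger). Removing the covariate alone would leave the Week 13 SE too small.
4. For each outcome, estimate Week 13 minus Week 1 and Week 25 minus Week 1 with 95% confidence intervals.
5. Either state a multiplicity rule, for example Holm across the two contrasts of each outcome, or label the contrasts as preliminary estimates with no significance claim.
6. Include all enrolled participants with a baseline measurement, since Week 1 is an outcome in this model.

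Items 2 and 4 are the core correction. The Kenward-Roger method and the choice of Holm are reasonable options, not the only ones.

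**Cost.** A few lines of text and Proc Mixed code, and no new data. The model has six covariance parameters instead of four. With complete data the contrasts equal paired t tests. In the central case (20000 data sets), two unadjusted contrasts give at least one false positive in 8.5% of data sets, and Holm gives 4.3%. For a 0.5 SD gain kept at both weeks, Holm lowers power from 97% to 96% at Week 13 and from 93% to 92% at Week 25.

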9.3 Informed Consent	13
9.4 Health Insurance Portability and Accountability Act (HIPAA)	14
9.5 Release of Information	14
9.6 Study Documentation	14
9.7 Records Retention and Requirements	14
9.8 Safety Monitoring	14
9.8.1 Data and Safety Monitoring	14
9.8.2 Protocol Violations Reporting and Management	14

9.8.3 Subject Confidentiality/Privacy 15

9.8.4 Adverse Events (AEs) and Serious Adverse Events (SAEs) 15

9.8.5 Definitions of Adverse Event and Serious Adverse Event 15

9.8.6 Non-Reportable Adverse Event and Serious Adverse Events 15

10.0 DATA MANAGEMENT AND PROCEDURES 17

10.1 Data Collection Forms 17

10.2 Data Acquisition and Entry 17

11.0 HUMAN SUBJECTS PROTECTION 18

LIST OF ABBREVIATIONS

AE	Adverse Event
BMI	Body Mass Index
CDRCC	Center for Depression Research and Clinical Care
ERC	Ethics Review Committee
GCP	Good Clinical Practice
IRB	Institutional Review Board
MDD	Major Depressive Disorder
MOST	Multi-Phase Optimization Strategy
MVPA	Moderate-to-Vigorous Physical Activity
SAE	Serious Adverse Event

STUDY SUMMARY

Title	Increasing Physical Activity among Breast Cancer Survivors with Depression
Short Title	Physical Activity in Breast Cancer Survivors with Depression
Protocol Number	122015-072
Phase	N/A
Methodology	Pilot study of a physical activity intervention among breast cancer survivors with depression
Study Duration	25 weeks
Study Center(s)	Single-center, UT Southwestern Center for Depression Research and Clinical Care
Objectives	Evaluate the feasibility of implementing a multi-component physical activity intervention in breast cancer survivors with significant depressive symptoms.
Number of Subjects	50
Diagnosis and Main Inclusion Criteria	Eligible breast cancer survivors between 3 months and 5 years post-treatment. 1) Positive depression screen (PHQ-9 score > 8) or current antidepressant treatment 2) Report <150 minutes of weekly moderate-to-vigorous physical activity (MVPA) on the GPAQ 3) Physically able to engage in physical activity 4) Written and verbal fluency in English.
Statistical Methodology	A total of 50 patients will be enrolled in this pilot study. The primary objective of this study is to determine the feasibility of implementing a multi-component physical activity intervention among breast cancer survivors with depression. A preliminary analysis of changes in physical activity and depressive symptoms will be conducted following the physical activity intervention.

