3.0 STUDY DESIGN

3.1 Overview of Study Design

The research project is a pilot study to assess the effects of a multi-component intervention in increasing physical activity among breast cancer survivors with depression. Breast cancer survivors listed in the UT Southwestern Simmons Cancer Center cancer registry will be contacted via mail and invited to complete a brief online questionnaire. Those indicating insufficient levels of physical activity and increased depressive symptoms will be invited to participate. The 12-week physical activity intervention will consist of three evidence-based strategies: print-based materials, active living classes, and activity self-monitoring.

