3.2 Duration of Study and Study Timeline

Recruitment of participants will begin in February 2016. We aim to recruit a cohort of 10 subjects in per month through June 2016 for a total of 50 subjects.

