4.3 Participant Recruitment and Retention

Based on previously published work utilizing contact of breast cancer survivors from the cancer registry system,¹⁷ we anticipate that approximately one-third (33%) of the contacted survivors (n=150) will return the questionnaire and agree to future contact to learn more about further physical activity interventions. Based on indications of physical activity frequency from the screening questionnaire, we will invite those who meet eligibility criteria (estimated to be at least 33% of respondents [n=50], based on national prevalence of sedentary behavior and depression among breast cancer survivors) to attend an initial in-person screening and baseline assessment session.

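### The Aim 3 model excludes enrolled participants with neither a Week 13 nor a Week 25 outcome, although their baseline values are collected and could be used

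*Combined protocol and SAP*

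**What the plan says.** Section 8.1 sets the sample for the mixed model of MVPA minutes and QIDS score: "The analysis will use all available data from all randomized patients with at least one post-baseline visit". It calls this a modified intent-to-treat sample. Time has three levels (Weeks 1, 13 and 25). The baseline value of the outcome is also a covariate, and the hypothesis is tested by the time effect. On testing, "all tests will be two-sided with alpha of .05 used for significance".

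Section 5.4 fixes when outcomes exist: "During the trial, the outcome assessments will be obtained at Weeks 1, 13, and 25". The table in Section 6.1 and the accelerometer text in Section 6.2.3 agree. Section 3.1 gives the programme length: "The 12-week physical activity intervention will consist of three evidence-based strategies". The first post-baseline outcome therefore falls just after the programme ends. The monthly contacts in Section 6.2.2 cover only contact details and medication changes.

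Section 5.5 says that participants who must stop the intervention are still asked to attend assessments. Appendix 1, Section 5.0 makes a similar request of those who withdraw from treatment. Section 5.4 allows some assessments by phone, mail, off-site or online.

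Section 8.1 lists retention as a feasibility criterion. The documents state no expected dropout rate, missing-data assumption or sensitivity analysis.

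**The concern.** The study has one arm, and Aim 3 rests on within-person change over time. No control group is there to absorb selective loss, so whoever is missing from the sample shapes the estimate directly.

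The people excluded are those with a baseline value and nothing afterwards. Week 1 is already a level of the time factor, and a likelihood-based repeated-measures model can use a participant who has only that value. Excluding them discards collected data and demands a stronger assumption. Loss must be unrelated to baseline level as well as to change, whereas the model with Week 1 as a response tolerates loss that depends on baseline.

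The covariate matters here. If baseline enters only as a covariate, a baseline-only participant has no response row and contributes nothing, even if the sample definition is widened. If it enters as both, the Week 1 response is conditioned on itself. Widening the sample therefore works only if the model is changed with it.

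At stake is a preliminary estimate that Section 2.1 says will support future grant applications. Section 8.1 calls these measures primary outcome measures.

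**Working it through.** **The plan's own figure.** The only sample-size figure is 50: "A total of 50 patients will be enrolled in this pilot study". It follows from recruitment: 10 per month x 5 months (February to June 2016) = 50, and 33% of 150 respondents = 49.5. There is no power calculation or dropout rate to reproduce, so the loss rates below are assumptions.

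**Who is excluded.** I read a visit as an assessment visit, since only those yield outcomes. The excluded group has a Week 1 value and no value at Week 13 or Week 25. An assumed 20% to 30% loss is 10 to 15 of 50, leaving 40 to 35.

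**Bias when loss depends on baseline.** Take equal SDs of 1 at both times, correlation r, true mean change D, share lost p, and baseline difference g (mean of those lost minus mean of those retained).

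- The retained baseline mean is p x g below the mean of all enrolled.
- Expected change given baseline is D - (1 - r) x (baseline - mean).
- So mean change in the retained set is D + p x g x (1 - r), and the bias is p x g x (1 - r).

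With r = 0.5 (assumed):

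- p = 0.20, g = 0.5: 0.20 x 0.5 x 0.5 = 0.05 SD
- p = 0.30, g = 0.8: 0.30 x 0.8 x 0.5 = 0.12 SD

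**Direction.** For depression, improvement is negative. If D = -0.22 and those lost were more depressed, the retained set shows -0.22 + 0.05 = -0.17 or -0.22 + 0.12 = -0.10. For activity, improvement is positive. If those lost were less active, g is negative and the estimate falls. Both understate improvement.

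**Simulation.** N = 50, two time points, SD 1, r = 0.5, true change -0.22, 4000 runs. The third column keeps all enrolled, with baseline as a response. The last sets change to zero in those lost.

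| Loss mechanism | Lost | Restricted set | All enrolled, likelihood | Zero change |
|---|---|---|---|---|
| Random | 20% | -0.223 | -0.223 | -0.179 |
| Random | 30% | -0.214 | -0.215 | -0.150 |
| Worse baseline leave | 20% | -0.135 | -0.220 | -0.108 |
| Worse baseline leave | 30% | -0.094 | -0.216 | -0.066 |
| Non-improvers leave | 20% | -0.385 | -0.347 | -0.308 |
| Non-improvers leave | 30% | -0.475 | -0.419 | -0.332 |

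The worse-baseline rows fit the formula. A bias of 0.085 at 20% implies g = 0.085 / (0.20 x 0.5) = 0.85 SD, slightly beyond the range used above.

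When non-improvers leave, the likelihood model removes only (0.385 - 0.347) / (0.385 - 0.22) = 23% of the bias at 20% lost, and (0.475 - 0.419) / (0.475 - 0.22) = 22% at 30%. The zero-change analysis moves the right way there, but the wrong way when loss is random or baseline-driven. That suits it to a sensitivity analysis, not the main one.

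**Zero-change arithmetic.** All-enrolled change = analysed change x (1 - share lost). For scale, the 70 minutes per week cited in Section 7.1 would become 56 at 20% lost and 49 at 30%.

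**The case against.** Several points on the other side stand.

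- **It is not a completer sample.** A reader might infer that anyone leaving the programme is removed, so that the label hides a near-completer analysis. The documents do not support that. Those who stop or withdraw are asked to stay in assessment, remote assessment is possible, and Section 5.6 pays for the Week 13 and 25 visits. A person who attended no class but supplied either outcome is analysed. These are requests, however, and do not change the rule for those who supply neither.
- **Inflated benefit does not follow.** A reader might assume that the restriction flatters the programme. If the more depressed or less active leave, it does the reverse.
- **The recommended model is no cure.** It recovers the truth when loss depends on baseline, but removes under a quarter of the bias when non-improvers leave. That is why a further sensitivity analysis is needed.
- **The size is modest and assumed.** At r = 0.5 the SD of change is 1, so with 40 to 35 analysed its standard error is 1/√40 = 0.16 to 1/√35 = 0.17 SD. The bias is about 0.3 to 0.7 of that. It should not be expressed as a share of the d = 0.22 in Section 1.0, which comes from randomised comparisons and is not a like-for-like denominator for uncontrolled change.
- **Aim 3 is preliminary.** Feasibility is the main objective, and retention is reported separately, so the loss is not hidden. That limits the weight of the point, but does not justify discarding baseline data when keeping them costs almost nothing.

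**Conclusion.** The point holds in a limited form. Enrolled participants with no Week 13 or Week 25 outcome are excluded from the Aim 3 change estimate although their baseline values are collected. The restricted set estimates mean change for all enrolled without bias only if loss is unrelated to baseline level and to change.

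Where loss depends on baseline, the bias is 0.05 to 0.12 SD under the assumed 20% to 30% lost, 0.5 to 0.8 SD baseline difference and correlation 0.5. The documents supply none of these inputs, so this is an illustration and not a forecast. The direction depends on who leaves: improvement is understated if those with worse baseline values go, and overstated if non-improvers go.

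Separately, the word *randomized* in the definition does not fit a study with one arm and no randomisation.

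**What to change.** In Section 8.1:

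1. Define the main Aim 3 set as all enrolled participants with a baseline value of the outcome, replacing *randomized* with *enrolled*.
2. Model Week 1 as a response, alongside Weeks 13 and 25, in the likelihood-based repeated-measures model, and remove baseline as a covariate. Items 1 and 2 must be made together.
3. Keep the at-least-one-post-baseline set as a sensitivity analysis.
4. Add a sensitivity analysis assuming zero change in those with no post-baseline outcome, since the main model only partly corrects for loss of non-improvers.
5. State the missing-data assumption, and report how many participants have no post-baseline outcome, with their baseline values.

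The cost is SAP wording and a small change to the Proc Mixed code. No new data, visits or participants are needed.

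### Aim 3 states a directional change at three and at six months for each outcome, but section 8.1 decides it by one two-sided time main effect and specifies no week-13 or week-25 contrast

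*Combined protocol and SAP*

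**What the plan says.** Section 2.0 (Study Objectives) describes Aim 3 as follows: "Conduct preliminary analysis of changes in physical activity and depressive symptoms following the physical activity intervention". Hypothesis 1 reads "Participants in the physical activity program will demonstrate increases in physical activity at three and six months". Hypothesis 2 says that participants "will demonstrate decreases in depressive symptoms at three and six months post-baseline". Each hypothesis therefore names a direction and two time points. The same section says of the pilot: "Results from this pilot project will support future grant applications".

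Section 8.1 (Primary Analyses) fits a mixed-effects repeated measures model to minutes of MVPA and to the depression score, which it calls the primary outcome measures. On time it says "The independent variables in the model will be time (weeks 1, 13, and 25)(within-subjects factor"), and on random effects "The model will allow for random slopes and intercepts". Higher-order time terms or log(time+1) may be brought in to improve fit. It adds "The baseline value of the dependent variable will be included as a covariate". All tests are two-sided at 0.05. The decision rule is "The hypothesis will be tested by the significance of the time effect main effect".

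No section specifies a week-13 or week-25 comparison with baseline, an estimate of change by visit, or a rule for combining the two visits.

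**The concern.** The test does not match the hypotheses. Each hypothesis makes two statements, one per visit, each with a sign. The rule gives one p-value per outcome. If that p-value is significant, the reader still does not know from the test which visit changed. Under a factor coding the reader does not know the direction either.

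The coding of time is also left open. The phrase about a within-subjects factor points to three categories. The random slopes and the higher-order or log terms point to continuous time. The null hypothesis under test differs between these. Baseline also appears twice, as week 1 among the time levels and as a covariate.

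What is at stake is the usefulness of the Aim 3 result. A later grant application needs the size of the change at each visit and its precision. The plan does not commit to producing either.

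**Working it through.** **No plan figure to reproduce.** The documents give no effect size, SD, correlation, dropout rate or power for Aim 3. The only input they supply is the enrolment target of 50 (Study Summary). The rest is assumed: complete data, a change of 0.5 SD, equal variances, and a common within-person correlation ρ of 0.5 (range 0.3 to 0.7). Means are written as (week 1, week 13, week 25) in SD units.

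**Three-level factor (2 df).** The noncentrality is λ = n·Σ(μ − mean)²/(1 − ρ), with F on 2 and 98 df.
- Change at week 13 only, (0, 0.5, 0): Σ = 0.1667, so λ = 50 × 0.1667/0.5 = 16.7.
- Week 25 only, (0, 0, 0.5), both visits, (0, 0.5, 0.5), and a worsening at both, (0, −0.5, −0.5), have the same Σ and so the same λ.
- All four reject in 96% of trials (87% at ρ = 0.3, 99.8% at ρ = 0.7). The test cannot tell them apart.

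**Linear time (1 df).** Weeks 1, 13 and 25 centre to −12, 0 and 12, so the fitted slope is (week 25 − week 1)/24 and week 13 has no weight. For a contrast c the noncentral t has 49 df and δ = c·μ·√n/√((1 − ρ)Σc²).
- Week 13 only: δ = 0, rejection 5%.
- Week 25 only: δ = 0.5 × √50/√(0.5 × 2) = 3.54, rejection 93% (83% to 99%).
- Both visits: the same δ and the same 93%.

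**log(time+1) (1 df).** The logs of 2, 14 and 26 centre to −1.50, 0.44 and 1.06, in the ratio −1.42 : 0.42 : 1.00, with Σc² = 3.58.
- Week 13 only: δ = 0.5 × 0.442 × √50/√(0.5 × 3.58) = 1.17, rejection about 21%.

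The test has a sign, but it is one fixed mixture of the visits. A change at both visits is then implied by the assumed curve and is not tested.

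**Quadratic time.** If both terms are tested jointly, this is the factor test again. If only the first-order term on uncentred weeks is read as the time effect, its weights are proportional to (−38, 52, −14). Rejection is then about 97% for week 13 only, 18% for week 25 only and 80% for both. A gain at week 25 pulls this estimate the wrong way.

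**Result.** Under none of these codings does a significant time effect establish a change in the stated direction at week 13 and at week 25.

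**What separate contrasts would give.** Each visit-minus-baseline difference has SD √(2(1 − ρ)) = 1.0. The 95% CI half-width is 2.01 × 1.0/√50 = 0.28 SD (0.22 to 0.34), and power per contrast for 0.5 SD is 93%. By simulation (100,000 trials), both contrasts are significant in the stated direction in about 88% of trials for a sustained 0.5 SD change (73% to 99%).

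**The case against.** The strongest reply is that this is a pilot. Its primary objective is feasibility, Aim 3 is labelled preliminary, and no sample size or go/no-go rule depends on the time test. An overall time test followed by inspection of the visit means is a common structure. This stands, and it limits the weight of the point. It does not supply the missing contrasts: section 8.1 sets a formal significance rule and does not say that the visit means will be reported.

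A reader might infer four stronger points, which the documents do not support.

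- *The plan would count a worsening as success.* A 2-df test has no sign, but section 8.1 does not say that a worsening meets the hypothesis. The hypotheses in section 2.0 are directional, and the sign can be read from the fitted means. Two-sided testing is not an error in itself.
- *The rule declares success in 96% of trials when only one visit changes.* That holds for a factor or a jointly tested quadratic. With linear time a week-13-only change rejects in 5%, and with log time in about 21%. The text does not settle the coding.
- *Both visits are required for success.* Section 2.0 says three and six months without saying whether one alone would count. Requiring both is a natural reading, but the sponsor has to choose it.
- *The time effect compares only week 25 with week 13.* This would follow if week 1 were dropped from the outcomes because baseline is a covariate. Section 8.1 lists week 1 as a time level, which argues against that reading.

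**Conclusion.** The concern holds as a mismatch between the hypotheses and the test. For each outcome, one two-sided time main effect cannot show a change in the stated direction at each of two visits, whichever permitted coding is used. This conclusion follows from the form of the tests and needs no assumed effect size.

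The percentages are illustrations. They rest on 50 complete participants, a 0.5 SD change, a common correlation of 0.3 to 0.7 and equal variances, none of which the documents give apart from the 50. They use a simple correlation pattern and not a full random-slopes model. No overall loss of power is claimed for the plan.

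The importance is minor to moderate. The effect is on how a preliminary result is read and reused, not on a confirmatory decision.

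**What to change.** Amend section 8.1 as follows.

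1. Enter time as a three-level factor (weeks 1, 13, 25).
2. Use baseline once: as a time level, or as a covariate with change from baseline at weeks 13 and 25 as the outcome.
3. For MVPA and for the depression score, prespecify week 13 minus baseline and week 25 minus baseline, each with its estimate and 95% CI, as the Aim 3 result in place of the overall time test.
4. State whether both visits are required or either suffices. If both, test each two-sided at 0.05 with no alpha split; a visit with no true change then passes in the stated direction in at most 2.5% of trials. If either suffices, use 0.025 each, because at 0.05 each the familywise error is about 9% per outcome.

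The change is to wording only and needs no new data. The cost is power under the both-visits rule. For a sustained 0.5 SD change at ρ = 0.5, joint power is 88.3%, against 93.4% for a single slope (5.1 points lower) and 95.8% for the 2-df test (7.5 points lower). Joint power falls to 79% if only 40 participants have all visits, and to 67% for a 0.4 SD change with 50. If the d of 0.22 cited in section 1.0 applied to this within-person change (an assumption), joint power would be 18% (12% to 34%), against 33% (25% to 50%) for one contrast. In that case the estimates and intervals would carry the result, which suits a pilot.
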